4.11.4 Vital Signs

All vital signs (height, weight, body temperature, respiratory rate, heart rate, systolic blood pressure, and diastolic blood pressure) will be assessed according to Protocol 7.4 - schedule of assessments.

Actual value, change from baseline, and percent change from baseline at each visit (timepoint if applicable) will be presented using descriptive statistics by DLs/arm in each phase.

All vital signs data will be presented in a data listing.

4.11.5 12-Lead Electrocardiograms

Electrocardiogram (ECG) parameters (heart rate, PR interval, QRS duration, QT interval, corrected QT interval [QTc]B, and QTcF) will be assessed according to Protocol 7.4 - schedule of assessments.

Actual value, change from baseline, and percent change from baseline at each visit (timepoint if applicable) will be presented using descriptive statistics by DLs/arm in each phase.

The QTcF interval will be summarized by the frequencies of subjects with absolute value and/or change from baseline using the criteria identified below:

- ≤ 450
- $> 450 - 480$
- $> 480 - 500$
- > 500
- ≤ 30 increases from baseline
- 30 to ≤ 60 increases from baseline
- > 60 increases from baseline

Subjects with abnormal ECG results, regardless of clinical significance, will be identified in data listings with flags for abnormalities.

4.11.6 Eastern Cooperative Oncology Group Performance Status

ECOG will be summarized over time as categorical variable and a shift table from baseline to worst post baseline will be provided.

All ECOG data will be presented in a data listing.

4.11.7 Physical Exam

Physical exam data will be presented in a data listing.

4.12 Biomarkers

A number of biomarkers will be assessed during the conduct of the study, including number, distribution, and phenotype of TILs, PD-L1 expression, and changes in TME.

TIL markers may include CD4, CD8, PanCK, and nuclear stain, among others. All TIL parameters (in vendor data of not listed here), PD-L1 expression, TME biomarkers will be summarized descriptively pre- and post-treatment in each arm by responder (CR or PR) vs. non-responder and PD vs. non-PD per RECIST and iRECIST, using the safety analysis set.

All biomarker results will be listed.

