#### 2.1.6. Ovarian Cancer

Ovarian Cancer (OC) is a potentially immunogenic tumor type that would likely benefit from immunotherapy since it has been shown that ovarian tumors with higher frequency of infiltrating lymphocytes are associated with better survival (31, 32) while higher PD-L1 expression at the tumor level is associated with poor prognosis (33). However, despite the high rate of tumor infiltrating lymphocytes (TILs), pembrolizumab monotherapy in patients with advanced recurrent

OC had limited efficacy with an ORR of 7.4-9.9% and a median PFS of 2.1 months ([\(34\)](#), NCT02674061), suggesting that blockade of the PD-1:PD-L1 axis is not sufficient to overcome the immunosuppressive tumor microenvironment (TME) in most OC patients. As a T-cell amplifier, NT-I7 has demonstrated its ability to expand T cells and promote tissue infiltration of lymphocytes in the TME of cancer patients. Thus, combination strategies including NT-I7 will likely increase the depth and breadth of the response to PD-1:PD-L1 blockade and thereby improve treatment efficacy.

In addition, preliminary data from the Dose Escalation phase (Phase 1b) of this study, NIT-110/KEYNOTE A60, showed significant increase of TILs in a subject with Clear Cell Ovarian Cancer.

Altogether, OC is well positioned to benefit from combination strategies that overcome the immunosuppressive TME. Including OC in this study potentially addresses a high unmet medical need for these patients. Furthermore, using OC as a model to determine the enhanced effects of pembrolizumab in combination with NT-I7 will provide relevant knowledge about pan-cancer biomarkers that may be used as predictors of anti-tumor activity.

**Conclusion:** Although immunotherapy has become new paradigm in cancer treatment, especially for tumors that are considered responsive to CPIs, the majority of patients fail to respond, and most responders eventually relapse. For tumors that are considered non-responsive to CPIs, such as MSS-CRC and PC, response to single-agent CPIs has been dismal. Thus, novel combinatorial strategies are needed to increase the depth and breadth of the response to CPIs.

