1.1.1 Primary Objectives

Phase 1b:

- To determine the safety and tolerability, including determination of the MTD and/or the RP2D of NT-I7 in combination with pembrolizumab in subjects with advanced solid tumors.

Phase 2a:

- To assess the preliminary anti-tumor activity of NT-I7 in combination with pembrolizumab in subjects with CPI treated R/R tumors (TNBC, NSCLC, SCLC), and CPI naïve R/R tumors (MSS-CRC, and PC), based on objective response rate (ORR) as assessed by Response Evaluation Criteria in Solid Tumors (RECIST) 1.1 and immune Response Evaluation Criteria in Solid Tumors (iRECIST).

Biomarker Cohort:

- To assess a potential correlation between tumor infiltrating lymphocytes (TILs) and clinical benefits in subjects with CPI-naïve R/R OC.

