1.2 Endpoints

1.2.1 Primary Endpoints

Phase 1b:

- Incidence, nature, and severity of adverse events (AEs) graded according to National Cancer Institute-Common Terminology Criteria for Adverse Events (NCI-CTCAE) v5.0.
- Incidence and nature of dose limiting toxicities (DLTs).
- Potential correlation of dose levels (DLs) with safety and efficacy parameters.

Phase 2a:

- ORR for each individual arm, defined as the percentage of subjects who have at least one confirmed partial response (PR) or complete response (CR), per RECIST 1.1 and iRECIST as determined by the investigator.

Biomarker Cohort:

- Number, distribution, and phenotype of TILs. CD8+TILs in tumor biopsy samples will be identified using a validated immunohistochemistry (IHC) assay and properly certified by a pathologist.

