4.9.4 Secondary Efficacy Endpoints Analysis for Phase 1b/2a/Biomarker Cohort

4.9.4.1 Objective Response Rate per RECIST 1.1 and iRECIST as determined by the Investigator for Biomarker Cohort

The same definition is followed as that for primary endpoint.

Exact two-sided 95% CIs for the ORR/iORR will be calculated using Clopper-Pearson method.

In addition, the following figures will be provided for each phase/arm, as applicable.

- Waterfall plot for best percentage change of target lesion size from baseline (maximum decrease, or minimum increase if no decrease)
- Swimmer plot for treatment duration and response
- Spider plot for the change of target lesion from baseline

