6. CHANGES FROM ANALYSIS PLANNED IN THE PROTOCOL

Analysis is added:

- Exploratory analysis of pre- and on-treatment tumor biopsy samples from the same organ will be performed and compared between responders vs. non-responders and PD vs. non-PD to help elucidate changes in TILs, PD-L1 expression, and TME biomarkers that may be correlated with treatment response.

Analyses are excluded:

- Expression of IFN- γ and associated inflammatory gene expression in the TME.
- Changes in peripheral blood biomarkers, including but not limited to immunophenotyping and inflammatory mediators, will be analyzed in association with 1) the incidence of AEs and 2) as surrogated markers of response, TME changes and TIL infiltration.

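### The Biomarker Cohort's primary objective is a TIL-benefit correlation, but the SAP plans only descriptive TIL summaries by responder and PD status, with no measure of association on the continuous scale

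*SAP*

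**What the plan says.** SAP 1.1.1 gives the cohort one primary objective: "To assess a potential correlation between tumor infiltrating lymphocytes (TILs) and clinical benefits in subjects with CPI-naïve R/R OC". Protocol 15.5 lists that correlation itself under the cohort's primary endpoint.

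The primary endpoint in SAP 1.2.1 is a TIL measurement only: "Number, distribution, and phenotype of TILs. CD8+TILs in tumor biopsy samples will be identified using a validated immunohistochemistry (IHC) assay". It contains no benefit variable and no measure of association.

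SAP 4.12 is the analysis section. TIL parameters are summarised descriptively before and after treatment in each arm, "by responder (CR or PR) vs. non-responder and PD vs. non-PD per RECIST and iRECIST", on the safety analysis set. SAP Section 6 adds an exploratory look at paired biopsies, "compared between responders vs. non-responders and PD vs. non-PD to help elucidate changes in TILs, PD-L1 expression, and TME biomarkers".

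SAP 1.3.5 sets the cohort at up to 10 evaluable subjects. The Protocol synopsis says this is meant to yield at least 4 evaluable pairs.

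A continuous measure of response is already planned as a figure in SAP 4.9.4.1: "Waterfall plot for best percentage change of target lesion size from baseline".

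**The concern.** The objective names a correlation, but the SAP gives no coefficient, no regression, no definition of the TIL change to be used and no definition of clinical benefit. Benefit enters only as two yes/no groupings. Section 6 lists changes from the protocol and does not say that a correlation was dropped, so this reads as an omission and not a declared choice.

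Two things are at stake. First, one of the two groupings may hold nobody or a single subject. Second, with 10 subjects or fewer, a grouping treats a deep response like a marginal one and a small increase like a near-response. Without a prespecified TIL metric and benefit variable, any association reported later could also be picked from many candidate pairs.

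**Working it through.** The documents state no power, precision or sample-size figure for this cohort, so there is none to reproduce.

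**Inputs**
- n = 10, the maximum number of evaluable subjects (SAP 1.3.5), and n = 4, the minimum target for pairs (Protocol synopsis).
- Response rate: Protocol 2.1.6 says pembrolizumab monotherapy in recurrent ovarian cancer "had limited efficacy with an ORR of 7.4-9.9" percent. This is not a planning value for the combination. For a range I also use 11.1% (3/27 per iRECIST in Arm IV, a different tumour, Protocol 2.3) and 21% (the Phase 2a alternative, which does not apply to this cohort).

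**Chance that the responder group is empty:** P(0) = (1 - p)^n

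| Response rate p | n = 10 | n = 4 |
|---|---|---|
| 7.4% | 0.926^10 = 46.4% | 0.926^4 = 73.5% |
| 9.9% | 0.901^10 = 35.3% | 0.901^4 = 65.9% |
| 11.1% | 0.889^10 = 30.8% | 0.889^4 = 62.5% |
| 21% | 0.79^10 = 9.5% | 0.79^4 = 39.0% |

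**Chance of at most one responder in 10:** P(0) + 10p(1 - p)^9 = 83.4% at 7.4%, 74.0% at 9.9% and 34.6% at 21%. With one responder against nine others, the smallest possible two-sided exact Mann-Whitney p is 2/10 = 0.20.

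**Chance that both PD groups are filled:** if 60% had PD (assumed), 1 - 0.4^10 - 0.6^10 = 99.4% at n = 10 and 1 - 0.4^4 - 0.6^4 = 84.5% at n = 4.

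**What a rank correlation could deliver**
- With 4 pairs there are 4! = 24 orderings, so the smallest exact two-sided p is 2/24 = 0.083. It cannot fall below 0.05.
- Approximate 95% interval for an observed coefficient of 0.7, by Fisher's transformation tanh(atanh 0.7 ± 1.96/√(n - 3)), with atanh 0.7 = 0.867: at n = 4, tanh(0.867 ± 1.96) = -0.80 to 0.99. At n = 10, tanh(0.867 ± 0.741) = 0.13 to 0.92.

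**Illustrative information loss at n = 10.** I simulated 4,000 bivariate normal samples per row, assuming 8.7% responders and 60% PD. Entries are the chance of p < 0.05 for Spearman's test and for an exact Mann-Whitney test on each split. The SAP proposes none of these tests, so the comparison only shows how much each summary retains.

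| Assumed true correlation | Spearman | PD split | Responder split |
|---|---|---|---|
| 0.7 | 58% | 32% | 9% |
| 0.5 | 28% | 14% | 4% |
| 0.3 | 12% | 7% | 2% |

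The ordering is the same in every row, but at 0.5 or below even the rank correlation would usually not reach p < 0.05.

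**The case against.** The strongest reply is that an association analysis does exist. Protocol Table 1 and SAP 1.2.3 compare responders with non-responders to look for tumor microenvironment changes correlated with response, and SAP Section 6 extends that to TILs and adds PD vs non-PD. PD vs non-PD is close to the complement of disease control, a recognised form of benefit, and would almost always have subjects on both sides. This stands. A reader might infer that the cohort cannot answer its primary question, but an empty responder group does not imply that.

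A reader might also take 35-46% as the protocol's own expectation. It is not. It carries a monotherapy rate over to the combination, and Protocol 2.1.6 expects the combination to do better. The figure needs its range.

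The plan is also descriptive, so low power for a test is not a failing of it, and a correlation assumed at 0.7 is favourable and unsupported by the documents. That stands too: the simulation illustrates and does not score the plan.

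The remedy has its own limits. With 4 pairs it is nearly uninformative. Target-lesion change also ignores new and non-target lesions, either of which makes a subject PD under Protocol 13.4.3, so a shrinking target sum can coexist with progression. It should therefore not replace the PD split.

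Finally, all biomarker results and lesion measurements will be listed, so the relationship could be drawn later. That helps a reader of the listings but does not fix in advance which TIL metric and which benefit variable count.

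**Conclusion.** The concern holds in a limited form. The cohort's only primary objective is a correlation, and the SAP offers only descriptive summaries across two dichotomies, with no measure of association on the continuous scale. The PD split partly addresses the objective. The responder split may well not: the chance of no responder among 10 is 46%-35% if the monotherapy rate carries over, 31% at 11.1% and 9.5% at 21%, and with 4 pairs it is 74%-66% at the monotherapy rates. The loss of depth of response does not depend on the response rate.

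This is a worthwhile, low-cost improvement to a small descriptive cohort. The documents do not support a claim that the cohort is invalid, or that a correlation would make it confirmatory.

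**What to change.** Add one paragraph to SAP 4.12 for the Biomarker Cohort, before database lock:

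- Estimate Spearman's correlation with a 95% CI between the change in CD8+ TILs from the pre-treatment to the on-treatment biopsy and the best percentage change in target-lesion sum, in subjects with an evaluable pair.
- Show a scatter plot with each point marked by best overall response, identifying PD due to new or non-target lesions.
- Keep the responder and PD splits alongside it.
- State that the estimate is descriptive and will be very imprecise, and that with 4 pairs the smallest exact two-sided p is 0.083.
- If power is illustrated, show a range of assumed correlations and not 0.7 alone.

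The cost is one paragraph and one output. The lesion measure is already derived for the waterfall plot and paired biopsies are already mandatory in this cohort, so no new data are needed and treatment does not change.

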4.13 Immunogenicity

Samples for immunogenicity assays shall be collected pre-dose from all study subjects in Phase 1b, Biomarker Cohort, and up to 10 subjects in each of the arms of Phase 2a. Samples shall be collected pre-dose on C1D1, C2D1, C3D1, and C5D1. Thereafter, samples shall be collected pre-dose on every 4 cycle such as C9D1, C13D1, C17D1, C21D1, and so on.

Incidence of ADA to NT-I7 during the study will be assessed, relative to the prevalence of ADA at baseline. Immunogenicity to NT-I7 will be measured using a risk-based, tiered testing approach. This includes screening and confirmatory assays for binding ADAs, epitope-specific assays to characterize ADA reactivity to whole NT-I7 vs IL-7 domain, and a cell-based neutralizing ADA assay for IL7 bioactivity. Subject samples will be obtained

at baseline and over the course of treatment (to evaluate the prevalence and incidence of treatment-emergent/boosted ADA).

ADA will be summarized in tabular by the following categories:

- N (%) of subjects with ADA positive at baseline (i.e. ADA detectable in the C1D1 pre-dose sample)
- N (%) of subjects with ADA negative at baseline (i.e. ADA detectable in the C1D1 pre-dose sample)
- N (%) of subjects with post-dose ADA positive (i.e. ADA detectable in any pre-dose sample from Cycle 2 onward)
- N (%) of subjects with treatment-emergent ADA, defined as those subjects with a negative ADA result at baseline and one or more post-treatment (Cycle 2 onward) ADA-positive samples.
- Subjects with treatment-boosted ADA, defined as subjects with a positive baseline ADA result who had one or more post-treatment (Cycle 2 onward) ADA result with the titer increased at least 4-fold.

NT-I7 ADA at each visit will be summarized by timepoint, DL/arm of each phase using Safety Analysis Set.

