Samples for immunogenicity assays shall be collected pre-dose from all study subjects in Phase 1b, Biomarker Cohort, and in up to 10 subjects in each of the arms of Phase 2a. Samples shall be collected pre-dose on C1D1, C2D1, C3D1, and C5D1. Thereafter, samples shall be collected pre-dose on every 4 cycle such as C9D1, C13D1, C17D1, C21D1, and so on. Testing may be conducted as indicated above, and repeated at 90-day follow up visit, if positive at the end of treatment visit.

For sampling details of PK, please refer to [Table 3](#). Additional information on handling and shipping are provided in the *NT-I7 Laboratory Manual*.

Whole blood will be collected for the multispectral immunophenotyping to obtain absolute cell counts for CD4+ and CD8+ T-cell subsets and activation states, NK cells, B cells, and other cell types as necessary.

TCR-seq analysis will be performed on both whole blood (pre- and on-treatment) for all Phase 1b and selected Phase 2a arms - TNBC (Arm I), MSS-CRC (Arm IV and Arm IVa), PC (Arm V and Arm Va), and the Biomarker Cohort (only for subjects who have dose of NT-I7 increase to 1200  $\mu$ g/kg at C5D1). TCR-seq whole blood sample should be taken pre-dose at C1D1 visit. On-treatment whole blood sample should be taken at the same visit (pre- or post-biopsy) as on-treatment tumor biopsy collection (C2D15 $\pm$ 7 days).

End of Treatment visit will occur approximately anytime within 7 days after disease progression determination or treatment discontinuation.

Safety follow-up visits will be performed in clinic visit will be performed every 30 days and 90 days after last dose of treatment.

Optional tumor biopsy at Cycle 6, Day 15 ( $\pm$  7 days) only for CPI naïve R/R OC Biomarker Cohort (only for subjects who have dose of NT-I7 increase to 1200  $\mu$ g/kg at C5D1), CPI-naïve R/R MSS-CRC Arm IVa, and CPI-naïve R/R PC Arm Va.

Applicable only for CPI naïve R/R OC Biomarker Cohort (only for subjects who have dose of NT-I7 increase to 1200  $\mu$ g/kg at C5D1), CPI-naïve R/R MSS-CRC Arm IVa, and CPI-naïve R/R PC Arm Va.

Optional visit applicable only for the CPI naïve R/R MSS-CRC Arm IVa and CPI-naïve R/R PC Arm Va expansion cohorts.

Visit must be performed in person during Phase 1b for PK sampling and may be performed in clinic or by telephone during Phase 2a.

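### SAP 4.13 gives ADA-negative at baseline the definition of ADA-positive, and its post-dose positive row omits the End of Treatment sample, so the ADA rows do not nest

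*SAP*

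**What the plan says.** SAP 4.13 lists five ADA categories.

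- Baseline positive: "ADA positive at baseline (i.e. ADA detectable in the C1D1 pre-dose sample".
- Baseline negative: "ADA negative at baseline (i.e. ADA detectable in the C1D1 pre-dose sample".
- Post-dose positive: "post-dose ADA positive (i.e. ADA detectable in any pre-dose sample from Cycle 2 onward".
- Treatment-emergent: negative at baseline, with "one or more post-treatment (Cycle 2 onward) ADA-positive samples".
- Treatment-boosted: positive at baseline, with "one or more post-treatment (Cycle 2 onward) ADA result with the titer increased at least 4-fold".

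ADA is also to be summarised visit by visit.

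On sampling, SAP 4.13 names C1D1, C2D1, C3D1 and C5D1 and then says "Thereafter, samples shall be collected pre-dose on every 4 cycle such as C9D1, C13D1, C17D1, C21D1, and so on". It names no sample after treatment ends. The immunogenicity row of the protocol's Schedule of Assessments (Section 7.4) continues past that point, with marks at End of Treatment and at the 90-day safety follow-up. Footnote 18 of that schedule says that testing may be "repeated at 90-day follow up visit, if positive at the end of treatment visit". SAP 4.13 repeats the rest of footnote 18 but not that sentence. SAP Section 6, which lists changes from the protocol's planned analyses, mentions nothing on immunogenicity.

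**The concern.** The secondary endpoint is ADA incidence on study set against ADA prevalence at baseline, so the table needs a clean baseline split and a clear rule on which later samples count. As written, the two baseline rows cannot be told apart. The post-dose row uses a narrower set of samples than the treatment-emergent and treatment-boosted rows beside it. A programmer who follows the text would produce a post-dose count that leaves out scheduled results. A reader of the table could find a subject who developed ADA on treatment but is not recorded as positive after dosing.

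**Working it through.** The plan states no figure to reproduce. The check compares the definitions with each other and with the sampling schedule.

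**Inputs.** Row definitions: SAP 4.13. Sampling visits: Protocol 7.4, immunogenicity row and footnote 18. Cycle length of 3 weeks: Protocol 5.1. Sampled subjects: all in Phase 1b and the Biomarker Cohort, up to 10 per Phase 2a arm (footnote 18). Percentages are based on subjects without missing data (SAP 2.1).

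**Step 1, baseline rows.** Let k of N sampled subjects have detectable ADA at C1D1. Read literally, both rows equal k/N, and together they give 2k/N where they should give 1. For N = 10 and k = 1 the table would show 10% and 10%, where 1/10 = 10% and 9/10 = 90% are meant. For k = 0 it would show 0% and 0%.

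**Step 2, post-baseline rows.** Classify each subject by baseline result, any pre-dose result from Cycle 2 onward, and End of Treatment result: 2 × 2 × 2 = 8 patterns.

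| Baseline | Pre-dose, Cycle 2 on | End of Treatment | Post-dose positive as written | Positive in any of these post-dose samples |
|---|---|---|---|---|
| − | − | − | no | no |
| − | − | + | **no** | **yes** |
| − | + | − | yes | yes |
| − | + | + | yes | yes |
| + | − | − | no | no |
| + | − | + | **no** | **yes** |
| + | + | − | yes | yes |
| + | + | + | yes | yes |

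Two of the 8 patterns are missed. The (−, −, +) subject can meet the treatment-emergent definition. The (+, −, +) subject can meet the treatment-boosted definition if the titre has risen enough. Neither is post-dose positive, so neither group need be a subset of the post-dose positive group.

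**Step 3, who is affected.** It is subjects who stop between scheduled pre-dose samples.

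- After C5D1 the next pre-dose sample is C9D1, 4 × 3 = 12 weeks later. For a subject who stops in between, End of Treatment is the only scheduled sample after C5D1 while on or just off treatment.
- A subject who stops after C2D1 but before the C3D1 sample has one eligible pre-dose sample, C2D1.
- A subject who stops during Cycle 1 has none, and the words Cycle 2 onward may shut the End of Treatment sample out of the other two rows as well.

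**Step 4, size per subject.** In a Phase 2a arm with n ≤ 10 subjects in the denominator, one missed positive moves the row by 1/n ≥ 1/10, that is, at least 10 percentage points.

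**Step 5, the 90-day sample.** Under footnote 18 the 90-day test repeats a positive End of Treatment result. A subject who reaches it this way is already positive, so once End of Treatment is counted the 90-day result adds no new ever-positive subject by that route. Protocol 12.2 asks for follow-up samples whenever possible, so a few others may exist; the effect is small.

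**The case against.** The best reply is that both points are clerical and that little is lost. Much of it stands.

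- The missing negation is obvious from the row label. The treatment-emergent and treatment-boosted definitions refer to a negative or positive baseline result and do not use the faulty parenthetical. A reader might infer that those classifications are corrupted; the text does not support that.
- A reader might also infer that End of Treatment data drop out of the ADA analysis. They do not. The pre-dose limit sits in one of five rows, and the SAP's visit list (Section 2.4) includes End of Treatment and the safety follow-ups, so the by-visit summary can show them.
- It is tempting to say that half the post-dose data are lost in early stoppers. That holds only for someone who stops after C2D1 and gives no C3D1 sample. Protocol 6.4.1 has otherwise stable subjects with a first RECIST progression continue to the next scan, so many would reach C3D1. The documents give no proportion.
- The healthy-volunteer study (Protocol 2.4.1.2.1) found neutralising antibodies in 10/24 at 1 month and 11/24 at 2 months. That is one subject's difference on a different measure and says little about late onset. In the same study 22 of 24 (91.7%) developed ADA after one dose, so many subjects here may already be positive at C2D1 or C3D1.

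What remains is that the post-dose row, followed as written, gives a wrong count for a definable group, and nothing in the SAP says that the narrower window was intended.

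**Conclusion.** Two definitions in SAP 4.13 need correcting. The baseline-negative wording is a plain slip with a clear intended meaning. The post-dose positive row is a substantive inconsistency: it excludes a sample that the protocol schedules, differs without explanation from the neighbouring rows, and can understate post-dose positivity. Each subject positive only at End of Treatment changes the row by at least 10 percentage points in a Phase 2a arm with up to 10 sampled subjects. The number of such subjects is unknown and could be zero, so this is a possible understatement and not a measured bias. The conclusion assumes that the End of Treatment sample is collected and tested as the schedule indicates, and that pre-dose means a sample followed by a dose. The effect is confined to a descriptive secondary summary; the primary ORR tests and the sample size are untouched.

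**What to change.** Amend SAP 4.13 before database lock.

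1. Define baseline negative as ADA not detectable in the pre-dose C1D1 sample.
2. Define post-dose positive as ADA detectable in any sample taken after the first NT-I7 dose, including End of Treatment and any 90-day sample.
3. Use that same window for treatment-emergent and treatment-boosted ADA, replacing the Cycle 2 onward wording. This also covers a subject who stops in Cycle 1.
4. Add the End of Treatment and 90-day samples to the SAP's sampling paragraph, so that it matches protocol footnote 18.

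The cost is a few lines of text and the matching table specification. The samples are already scheduled, so no new collection is needed.
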